Please think about your typical weeks, did you engage in physical activity at least 5 days per week for 30 minutes or more (or 150 minutes during the week), in such a way that you were moderately exhausted?

1. No, and I do not intend to start.....
2. No, but I am considering it.....
3. No, but I seriously intend to start.....
4. Yes, but only for a brief period of time.....
5. Yes, and for a long period of time.....

2. Physical activity behaviour

We are interested in finding out about the kinds of physical activities that people do as part of their everyday lives. The questions will ask you about the time you spent being physically active in the last 7 days. Please answer each question even if you do not consider yourself to be an active person. Please think about the activities you do at campus, such as, to get from place to place, and in your spare time for recreation, exercise or sport.

Think about all the vigorous activities that you did in the last 7 days. Vigorous physical activities refer to activities that take hard physical effort and make you breathe much harder than normal. Think only about those physical activities that you did for at least 10 minutes at a time.

(1). During the last 7 days, on how many days did you do vigorous physical activities like heavy lifting, digging, aerobics, or fast bicycling?

_____ days

No vigorous physical activities

(2). How much time did you usually spend doing vigorous physical activities on one of those days?

_____ hours per day

_____ minutes per day

Think about all the moderate activities that you did in the last 7 days. Moderate activities refer to activities that take moderate physical effort and make you breathe somewhat harder than normal. Think only about those physical activities that you did for at least 10 minutes at a time.

(1). During the last 7 days, on how many days did you do moderate physical activities like carrying light loads, bicycling at a regular pace, or doubles tennis? Do not include walking.

_____ days

No moderate physical activities

(2). How much time did you usually spend doing moderate physical activities on one of those days?

_____ hours per day

_____ minutes per day

Think about the time you spent walking in the last 7 days. This includes at work and at home, walking to travel from place to place, and any other walking that you have done solely for recreation, sport, exercise, or leisure.

(1). During the last 7 days, on how many days did you walk for at least 10 minutes at a time?

_____ days

No walking

(2). How much time did you usually spend walking on one of those days?

_____ hours per day

_____ minutes per day

3. How high do you perceive your risk that at some point in the future ...

	Very unlikely			Moderately unlikely			Very likely
1. ... your levels of cholesterol will be too high	 ₁	 ₂	 ₃	 ₄	 ₅	 ₆	 ₇
2. you will suffer a heart attack	 ₁	 ₂	 ₃	 ₄	 ₅	 ₆	 ₇
3. ... your blood pressure will be too high	 ₁	 ₂	 ₃	 ₄	 ₅	 ₆	 ₇
4. ... you will suffer a stroke	 ₁	 ₂	 ₃	 ₄	 ₅	 ₆	 ₇
5. ... you will develop a heart disease	 ₁	 ₂	 ₃	 ₄	 ₅	 ₆	 ₇

4. Intention of physical activity

Which intentions do you have for the near future?

I intent to do for at least 30 minutes a day on minimum 5 days a week (or at least 150 minutes a week)...

	not true			exactly true
1. ... perform strenuous physical activity (heart beats faster, sweating)	 ₁	 ₂	 ₃	 ₄
2. ... be moderately physically active (not fatiguing, mild sweating)	 ₁	 ₂	 ₃	 ₄
3. ... be mildly physically active (hardly strenuous, no sweating)	 ₁	 ₂	 ₃	 ₄

5. Outcome expectancies of physical activity

If I am physically active 5 days a week for 30 minutes or more, then...

	Totally disagree				Totally agree
1. ... this is good for my health.	 ₁	 ₂	 ₃	 ₄	 ₅
2. ... I feel better afterwards.	 ₁	 ₂	 ₃	 ₄	 ₅
3. ... it will cost me a lot of time (e.g. changing clothes, reaching the sport venue).	 ₁	 ₂	 ₃	 ₄	 ₅
4. ... this will be a financial burden.	 ₁	 ₂	 ₃	 ₄	 ₅

6. Self-Efficacy of physical activity

Motivational Self-Efficacy

I feel certain that I can be physically active a minimum of 5 days a week for 30 minutes, ...

	Totally disagree				Totally agree
1... even if it is difficult.	 ₁	 ₂	 ₃	 ₄	 ₅

Maintenance Self-Efficacy

I feel certain that I can be physically active permanently a minimum of 5 days a week for 30 minutes, ...

	Totally disagree				Totally agree
2... even if it takes a lot of time till I am used to it.	 ₁	 ₂	 ₃	 ₄	 ₅
3... even if I have worries and problems (e.g. proposed date and time).	 ₁	 ₂	 ₃	 ₄	 ₅

Recovery Self-Efficacy

I feel certain that I can again be physically active a minimum of 5 days a week for 30 minutes, ...

	Totally disagree				Totally agree
4... even if I changed my concrete plans several times.	 ₁	 ₂	 ₃	 ₄	 ₅
5... even if I was not physically active for several weeks.	 ₁	 ₂	 ₃	 ₄	 ₅

7. Plans of physical activity

For the next month I already planned in detail ...

	Totally disagree				Totally agree
1. ... which concrete physical activity I will pursue (e.g. walking).	 ₁	 ₂	 ₃	 ₄	 ₅
2. ... where I will be physically active (e.g. in the gym).	 ₁	 ₂	 ₃	 ₄	 ₅
3. ... on which days I will be physically active (e.g. every Tuesday and Friday).	 ₁	 ₂	 ₃	 ₄	 ₅
4. ... when I have to be especially cautious not to stop being active.	 ₁	 ₂	 ₃	 ₄	 ₅
5. ... what I can do in difficult situations, in order to remain true to my own resolutions	 ₁	 ₂	 ₃	 ₄	 ₅
6. ... how I can stay active, even if something happened	 ₁	 ₂	 ₃	 ₄	 ₅

8. Perceived Social Support of physical activity

	not true			exactly true
1. My partner supports me to stay physically active	 ₁	 ₂	 ₃	 ₄
2. People from my family supports me to stay physically active	 ₁	 ₂	 ₃	 ₄

3. People like my classmates and friends helps me to stay physically active ₁ ₂ ₃ ₄

Part II Dietary Behaviour and Relevant Factors

1. Stage of change in dietary behavior

Please think about what you have typically consumed during the last 7 days, Did you eat five portions of fruit and vegetables per day?

1. No, and I do not intend to start.....
2. No, but I am considering it.....
3. No, but I seriously intend to start.....
4. Yes, but only for a brief period of time.....
5. Yes, and for a long period of time.....

2. Dietary behaviour

On how many days during the last 7days have you been eaten fruits and vegetables?

- Less than 1 day
- 1 day
- 2 days
- 3 days
- 4 days
- 5 days
- 6 days
- 7 days

On those days you ate fruits and vegetables, how many portions do you eat?

_____ portions (One portion accounts for approximately one hand of fruit or vegetable)

3. Intention of dietary behaviour

Which intentions do you have for the near future? I seriously intent to, ...

	not true			exactly true
1. ... eat at least 5 portions of fruit and vegetable daily .	 ₁	 ₂	 ₃	 ₄
2. ... eat fruit and vegetable at every meal.	 ₁	 ₂	 ₃	 ₄
3. ... drinking each day at least one glass of fruit- or vegetable juice	 ₁	 ₂	 ₃	 ₄

4. Outcome expectancies of dietary behaviour

If I daily eat 5 portions of fruit and vegetable, then ...

	Totally disagree				Totally agree
1. ... this is good for my health.	 ₁	 ₂	 ₃	 ₄	 ₅
2. ... I feel better afterwards.	 ₁	 ₂	 ₃	 ₄	 ₅

3. ... this will cost me a lot of time (e.g. buying, preparations).	 ₁	 ₂	 ₃	 ₄	 ₅
4. ... this will be a financial burden.	 ₁	 ₂	 ₃	 ₄	 ₅

5. Self-Efficacy of dietary behaviour

Motivational Self-Efficacy

I feel certain that I can eat at least 5 portions of fruit and vegetable a day, ...

	Totally disagree				Totally agree
... even if it is difficult.	 ₁	 ₂	 ₃	 ₄	 ₅

Maintenance Self-Efficacy

I feel certain that I can permanently eat 5 portions of fruit and vegetable a day, ...

	Totally disagree				Totally agree
1. ... even if it takes a lot of time till I am used to it.	 ₁	 ₂	 ₃	 ₄	 ₅
2. ... even if I have worries and problems (e.g. proposed date and time).	 ₁	 ₂	 ₃	 ₄	 ₅

Recovery Self-Efficacy

I feel certain that I can again eat 5 portions of fruit and vegetable a day, ...

	Totally disagree				Totally agree
1. ... even if I changed my concrete plans several times.	 ₁	 ₂	 ₃	 ₄	 ₅
2. ... even if I ate no or less fruits and vegetables on several days.	 ₁	 ₂	 ₃	 ₄	 ₅

6. Plans of dietary behaviour

For the next month I already planned in detail, ...

	Totally disagree				Totally agree
1. ... what I will eat (e.g. cereals, fruits).	 ₁	 ₂	 ₃	 ₄	 ₅
2. ... at which meals I will eat fruits and vegetables (e.g. additional salad).	 ₁	 ₂	 ₃	 ₄	 ₅
3. ... how I will prepare the food.	 ₁	 ₂	 ₃	 ₄	 ₅
4. ...when I have to pay attention not to fall into old eating habits	 ₁	 ₂	 ₃	 ₄	 ₅
5. ...what I can do in difficult situations, in order to remain true to my own resolutions	 ₁	 ₂	 ₃	 ₄	 ₅
6. ...how I can eat healthy, even if something happened	 ₁	 ₂	 ₃	 ₄	 ₅

7. Perceived social support of dietary behaviour

How do you perceive your environment?

	not true			exactly true
1. My partner supports me to eat healthy	 ₁	 ₂	 ₃	 ₄
2. People from my family supports me to eat healthy	 ₁	 ₂	 ₃	 ₄
3. People like my classmates and friends help me to eat healthy	 ₁	 ₂	 ₃	 ₄

Part III Variables Related to Health

1. Compensatory Health belief

	Totally disagree				Totally agree
1. I can compensate for not being very active by eating less.	 ₁	 ₂	 ₃	 ₄	 ₅
2. An unhealthy diet can be balanced by physical activity.	 ₁	 ₂	 ₃	 ₄	 ₅
3. If you are eating healthy it is not as important to be physically active.	 ₁	 ₂	 ₃	 ₄	 ₅
4. When you are physically active you can eat without many restraints.	 ₁	 ₂	 ₃	 ₄	 ₅

2. WHOQOL-BREF (general quality of life + physical domain)

	Very poor				Very good
1. How would you rate your quality of life?	 ₁	 ₂	 ₃	 ₄	 ₅
The following questions ask about how much you have experienced certain things in the last four weeks.	Not at all				An extreme amount
2. To what extent do you feel that physical pain prevents you from doing what you need to do?	 ₁	 ₂	 ₃	 ₄	 ₅
3. How much do you need any medical treatment to function in your daily life?	 ₁	 ₂	 ₃	 ₄	 ₅
The following question asks about how completely you experience or were able to do certain things in the last four weeks.	Not at all				An extreme amount
4. Do you have enough energy for everyday life?	 ₁	 ₂	 ₃	 ₄	 ₅
	Very poor				Very good
5. How well are you able to get around?	 ₁	 ₂	 ₃	 ₄	 ₅
	Very dissatisfied				Very satisfied
6. How satisfied are you with your sleep?	 ₁	 ₂	 ₃	 ₄	 ₅

-
7. How satisfied are you with your ability to perform your daily living activities? ₁ ₂ ₃ ₄ ₅
8. How satisfied are you with your capacity to work? ₁ ₂ ₃ ₄ ₅
-

Part IV Demographic factors

1. Your name: _____
2. Please indicate your sex: male/female
3. How old are you? _____
4. Body height: _____ cm; Body weight: _____ kg
5. Please indicate your marital status
 - Single
 - Close relationship, not living together
 - Close relationship, living together
 - Marital partnership/Common law marriage
6. Please indicate your study year.
 - Year 1
 - Year 2
 - Year 3
 - Year 4
7. Please indicate the name of your university
 - Wuhan University
 - Nantong University

亲爱的同学:

您好!

我们本次调查旨在了解您的健康状况和一些与体育运动行为、健康饮食行为相关的影响因素。您对以下调查所作的回答，并无正确和错误之分，我们只需要您的**真诚**回答。

下面呈现的问卷包含了四个方面的内容（1）体育运动行为和相关因子；（2）健康饮食行为和相关因子；（3）与健康状况有关的变量；（4）人口统计学变量。请仔细阅读每份问卷，并按要求回答。

感谢您的合作!

第一部分 体育运动行为及相关因子

1. 体育运动的阶段变化

您是否会进行每周至少 5 次，每次至少 30 分钟的中等强度体育运动？请您根据平时的情况进行选择。

- 1 我没有做到，也并未打算这样.....
- 2 我没有做到，但正考虑这样.....
- 3 我没有做到，但真的很想这样.....
- 4 我能够做到，但只持续了很短的时间.....
- 5 我能够做到，并且长期这样.....

2. 体育运动行为

我们想了解人们日常生活中会进行哪些体育运动。下述问题意在获悉您在过去 7 天所进行的体育运动情况，即使您认为自己不是一位积极参加体育运动的人，也请认真回答下面的每道题目。您所参加的可以是与学习有关的一些活动，也可以是在闲暇时从事的体育娱乐活动，可以在寝室或室外空地上进行的，也可以是在两地往返的过程中进行的（例如步行或者骑自行车往返）。

请您回想一下在刚刚过去的 7 天里，您所进行过的大强度的体育运动（非常消耗体能且呼吸明显比平时急促）每次持续时间至少为 10 分钟

- (1). 在这 7 天里，您有几天进行过大强度体育运动（例如，负担重物、大强度有氧运动、快速骑自行车等）？

_____ 天

我没有进行过大强度体育运动。

- (2). 您进行一次大强度体育运动的持续时间通常为多少？

_____ 小时/每天

_____ 分钟/每天

请您回想一下在刚刚过去的 7 天里，您所进行过的中等强度体育运动（适中的体能消耗，呼吸较平时略有急促）每次持续时间至少 10 分钟。

- (1). 在这 7 天里，您有几天进行过中等强度体育运动（例如，搬运较轻的物品、中等速率骑自行车、网球双打，但不包括散步）

_____ 天

我没有进行过中等强度体育运动。

- (2). 一次中等强度体育运动的持续时间通常为多少？

_____ 小时/每天

_____ 分钟/每天

请您回想一下在刚刚过去的 7 天里，您所进行过的低强度体育运动，例如，步行往返于两地，或者以休闲娱乐/体育锻炼为目的的散步。

(1). 在这 7 天里，您有几天进行过每次持续至少 10 分钟的散步？

_____ 天

我没有散步

(2). 每次散步的持续时间通常为多少？

_____ 小时/每天

_____ 分钟/每天

3. 下面的问题涉及到您对疾病的危险感知。请思考一下，您的身体今后出现下面问题的可能性有多大。请选择最符合您情况的选项。

	绝对 不会			有可能			完全 可能
1. 发生高脂血症的可能性	 1	 2	 3	 4	 5	 6	 7
2. 心脏病急性发作的可能性	 1	 2	 3	 4	 5	 6	 7
3. 发生高血压的可能性	 1	 2	 3	 4	 5	 6	 7
4. 发生中风的可能性	 1	 2	 3	 4	 5	 6	 7
5. 发生心血管病的可能性	 1	 2	 3	 4	 5	 6	 7

4. 对体育运动的意向

在不久的将来，哪种意向与您相符？

我打算进行....，一周 5 次，每次 30 分钟（每周持续时间至少为 150 分钟）

	完全 不符合			完全 符合
1 ...大强度的体育运动（心跳加速并且大量的汗）	 1	 2	 3	 4
2 ...中等强度的体育运动(会流汗但不会精疲力竭)	 1	 2	 3	 4
3 ...低强度的体育运动(费力很少且不会流汗)	 1	 2	 3	 4

5. 对体育运动的结果期待

如果我能做到每周至少 5 天，每次至少 30 分钟的体育运动，我认为...

	完全 不同意				完全 同意
1 ... 这有益于我的健康	 1	 2	 3	 4	 5

2 ... 我会感觉更好	 ₁	 ₂	 ₃	 ₄	 ₅
3 ... 这会耗用我过多时间(例如, 换衣服的时间, 往返于运动场所的时间)。	 ₁	 ₂	 ₃	 ₄	 ₅
4 ... 这将是经济负担	 ₁	 ₂	 ₃	 ₄	 ₅

6. 体育运动的自我效能

动机自我效能

我确信自己能完成每周至少 5 次, 每次至少 30 分钟的体育运动, 即使...

	完全 不同意				完全 同意
1 ... 在遇到诸多困难时	 ₁	 ₂	 ₃	 ₄	 ₅

保持自我效能

我确信自己能完成每周至少 5 次, 每次至少 30 分钟的体育运动, 并坚持下去, 即使...

	完全 不同意				完全 同意
2 ... 这会耗用我很多时间	 ₁	 ₂	 ₃	 ₄	 ₅
3 ... 当我遇到困扰或麻烦时 (例如, 有约会或时间另有安排)	 ₁	 ₂	 ₃	 ₄	 ₅

恢复自我效能

我确信自己能够再次完成每周至少 5 次, 每次至少 30 分钟的体育运动, 即使...

	完全 不同意				完全 同意
4 ... 当我多次改变运动项目时	 ₁	 ₂	 ₃	 ₄	 ₅
5 ... 当我有一段时间没有参加运动时	 ₁	 ₂	 ₃	 ₄	 ₅

7. 体育运动的计划

我已经为下个月进行体育运动制定了详细计划 ...

	完全 不同意				完全 同意
1. ... 在哪里运动	 ₁	 ₂	 ₃	 ₄	 ₅
2. ... 参加哪种运动	 ₁	 ₂	 ₃	 ₄	 ₅
3. ... 在哪几天运动	 ₁	 ₂	 ₃	 ₄	 ₅
4. ... 在特殊情况下, 怎样坚持运动 (如, 外出度假时, 定计划做运动)	 ₁	 ₂	 ₃	 ₄	 ₅

5. ...在困难情况下，怎样坚持运动（如，学业很忙时，抽出时间做运动） 1 2 3 4 5
6. ...在做运动时，遇到一些突然状况，怎样能继续坚持运动（例如，跑步时，突然下雨。这时可以回到家，继续做一些伸展运动） 1 2 3 4 5

8. 下列问题询问您在运动方面得到怎样的支持。

	完全 不符合			完全 符合
1. 我的伴侣（如：配偶或关系亲密的男朋友/女朋友）帮助我坚持做运动	 1	 2	 3	 4
2. 我的家人（如：兄弟姐妹，父母）帮助我坚持做运动	 1	 2	 3	 4
3. 我的同学和朋友帮助我坚持做运动	 1	 2	 3	 4

第二部分 健康饮食行为与相关因子

1. 健康饮食行为的阶段变化

您每天是否可以做到吃 5 份（一份约等于一把水果/蔬菜）水果和蔬菜？请您根据上周比较普遍的情况进行选择（单选）

1. 我没有做到，也并未打算这样.....
2. 我没有做到，但正考虑这样.....
3. 我没有做到，但真的很想这样.....
4. 我有能够做到，但只持续了很短的时间.....
5. 我有能够做到，并长期这样.....

2. 健康饮食行为

在刚过去的 7 天，您有几天吃过吃水果和蔬菜？

- 不到 1 天
- 1 天
- 2 天
- 3 天
- 4 天
- 5 天
- 6 天
- 7 天

当您吃水果或蔬菜时，您会吃__份（一份约等于一把水果/蔬菜）

3. 对健康饮食行为的意向

在不久的将来，哪种意向与我相符，我打算...

	完全 不符合			完全 符合
1. ... 每天至少吃 5 份水果和蔬菜 .	 ₁	 ₂	 ₃	 ₄
2. ...每餐都吃水果和蔬菜	 ₁	 ₂	 ₃	 ₄
3. ... 每天都至少喝一杯果汁或蔬菜汁	 ₁	 ₂	 ₃	 ₄

4. 对健康饮食行为的结果期待

如果我每天都吃 5 份水果和蔬菜，那么，我认为...

	完全 不同意				完全 同意
1. ... 这有益于我的健康	 ₁	 ₂	 ₃	 ₄	 ₅
2. ... 我会感觉更好	 ₁	 ₂	 ₃	 ₄	 ₅
3. ... 这会耗用我过多时间 (例如，购买水果和蔬菜所耗用的时间)	 ₁	 ₂	 ₃	 ₄	 ₅
4. ... 这将是个经济负担	 ₁	 ₂	 ₃	 ₄	 ₅

5. 健康饮食行为的自我效能

动机自我效能

我确信自己每天都能吃 5 份水果和蔬菜，即使...

	完全 不同意				完全 同意
1 ...在遇到诸多困难时	 ₁	 ₂	 ₃	 ₄	 ₅

保持自我效能

我确信自己每天都能吃 5 份水果和蔬菜，并坚持下去，即使...

	完全 不同意				完全 同意
2 ... 我需要花很长时间去适应这样的饮食习惯	 ₁	 ₂	 ₃	 ₄	 ₅
3 ... 当我遇到困扰或麻烦时 (例如，有约会或时间另有安排).	 ₁	 ₂	 ₃	 ₄	 ₅

恢复自我效能

我确信自己能够再次完成每天吃 5 份水果和蔬菜，即使...

	完全不同意				完全同意
4. ...当我多次改变饮食计划时	 ₁	 ₂	 ₃	 ₄	 ₅
5. ... 当我有几天没有做到（没吃，或吃的量不够）时	 ₁	 ₂	 ₃	 ₄	 ₅

6. 健康饮食行为的计划

我已经为下个月制定了详细计划...

	完全不同意				完全同意
1. ...在哪一餐吃水果和蔬菜	 ₁	 ₂	 ₃	 ₄	 ₅
2. ...吃什么水果和蔬菜	 ₁	 ₂	 ₃	 ₄	 ₅
3. ...用什么方法准备水果和蔬菜（例如，榨果汁，蒸煮或炒蔬菜）	 ₁	 ₂	 ₃	 ₄	 ₅
4. ...特殊情况下怎样避免不良饮食习惯（例如，外出度假期间，尽量多吃蔬菜和水果）	 ₁	 ₂	 ₃	 ₄	 ₅
5. ...在困难情况下，怎样能坚持健康饮食的意向（例如，学业很忙时，抽时间吃水果）	 ₁	 ₂	 ₃	 ₄	 ₅
6. ...在健康饮食过程中，当遇到一些突然状况，怎样能吃得健康（例如，与同学或朋友在外聚餐时，尽量多吃蔬菜和水果）	 ₁	 ₂	 ₃	 ₄	 ₅

7. 可知觉到的健康饮食行为的社会支持

	完全不符合				完全符合
1. 我的伴侣（如配偶，关系亲密的男朋友/女朋友）帮助我坚持健康饮食	 ₁	 ₂	 ₃	 ₄	 ₄
2. 我的家人（如：兄弟姐妹，父母）帮助我健康饮食	 ₁	 ₂	 ₃	 ₄	 ₄
3. 我的同学和朋友帮助我吃得健康	 ₁	 ₂	 ₃	 ₄	 ₄

第三部分 与健康状况有关的变量

1. 下面是询问您如何看待饮食和运动之间的关系。

	完全不同意				完全同意
1. 少进食可以弥补运动不足	 ₁	 ₂	 ₃	 ₄	 ₅
2. 体育运动可以平衡不健康的饮食行为	 ₁	 ₂	 ₃	 ₄	 ₅
3. 只要饮食健康，积极参加体育运动也不是这么重要的	 ₁	 ₂	 ₃	 ₄	 ₅

4. 当运动量足够时，就可以毫无顾忌地进食。 ₁ ₂ ₃ ₄ ₅

2. 生存质量测定量表

	非常差				非常好
1. 您如何评价自己的生活质量?	 ₁	 ₂	 ₃	 ₄	 ₅
在刚过去的四周内，你在多大程度上经历了下述情况	完全不符合				完全符合
2. 身体疼痛在多大程度上影响到您?	 ₁	 ₂	 ₃	 ₄	 ₅
3. 您生活中多大程度上依赖于药物治疗?	 ₁	 ₂	 ₃	 ₄	 ₅
在刚过去的四周内，你在多大程度上经历了（或能够做到）下述情况	完全不符合				完全符合
4. 您生活中充满活力吗?	 ₁	 ₂	 ₃	 ₄	 ₅
	非常差				非常好
5. 您是否可以随意活动?	 ₁	 ₂	 ₃	 ₄	 ₅
	非常不满意				非常满意
6. 您对自己的睡眠质量满意吗?	 ₁	 ₂	 ₃	 ₄	 ₅
7. 您对自己处理日常生活事情的能力满意吗?	 ₁	 ₂	 ₃	 ₄	 ₅
8. 您对自己的工作能力满意吗?	 ₁	 ₂	 ₃	 ₄	 ₅

第四部分 人口统计学变量

1 姓名： _____

2 性别： 男 女

3 年龄： _____

4 你目前的身高是： _____厘米； 体重是： _____公斤

5 您的婚姻状况

- 单身
- 亲密关系，但没有一起生活
- 有亲密关系并且一起生活
- 法定婚姻关系

6 您的年级是？

- 本科一年级
- 本科二年级
- 本科三年级
- 本科四年级

7. 您就读的大学是：

- 武汉大学
- 南通大学

7. Expected duration : 19 months

Proposed starting date: 1 Jun 2016

Expected completion date: 31 Dec 2017

8. Estimated cost of the whole project (in Hong Kong dollars):

				Year 1	Year 2	Total
(a)	Staff* Rank	Salary per month	No. of Months			
	Research Assistant(Pt.4) X 1	\$10,908	10.0	\$109,080.0	\$0.0	\$109,080. 0
(b)	Equipment (please itemise and include cost of computing equipment in the budget total)					
(c)	General Expenses** (please itemise)					
	(1) Website set-up			\$18,000	\$0	
	(2) Promotional materials			\$3,000	\$0	
	(3) Transportation and accommodation expenses			\$9,920	\$0	
						\$30,920
(d)	Conference / Publication** (see Note)					
	conference and publication charges			\$10,000	\$0	\$10,000
Total:				\$150,000.0	\$0.0	\$150,000.0

* FRG normally supports research support staff at the Research Assistant level.

** PI should include the cost for the medical surveillance programme for research personnel that would involve the use of organophosphate and 2,3,7-8 TCDD as well as other highly toxic chemicals suggested by the Laboratory Safety Sub-Committee. For programme details, please contact the EHSU of the Estates Office.

Note: With effect from the 2011/2012 academic year, FRG supports conference and publication charges up to \$10,000 for PI to attend recognized international conference and to disseminate the research results.

9. (a) Justifications for each category/item of the budget in Item 8 above:

(Regarding 8(a), list the duties and time involved for the research support staff required. Also list the division of work / duties between the PI and the research support staff).

Staff Cost:

A full-time research assistant will be employed for 10 months. S/he will assist website set-up and function test (4 months), main study implementation (4 months), data management and analysis, and report writing (2 months) .

Equipment Cost:

General Expenses:

(1) An e-health learning website will be set up by a website production company in Wuhan, China. In addition, the SMS group message service will be included in this website platform.

(2) For participant recruitment, flyer will be made and distributed to university students at their PE classes. The content of flyer includes program introduction and online registration hyperlink. 3,000HK\$ in total.

(3) PI may need to visit Wuhan University and Nantong University for promoting the study.

Conference and Publication Cost :

This research topic is very popular in the field of health promotion. The investigators would like to attend an international conference and publish one article to disseminate the research results.

9. (b) Facilities and major equipment already available in addition to those requested in Item 8(b)

A work station, with a computer set will be provided to Research Assistant. No extra equipment will be needed in this project.

10. Other research funds that have already been obtained from other sources for this project (if any):

(Please give source(s) of funding and amount.)

11. Allocation for Faculty Research Grant Requested:

(Item 11 = Item 8 - Item 10)

\$ 150,000

12. Have funds been sought previously for the same or similar project(s)? If so, please state:

Organisation/ Committee applied to:	
Project Code:	
Project Title: (if different from item 1 above)	
Date of Application:	
Outcome:	

NOTE: If this proposal is similar to a proposal that has been submitted to the RGC or other funding bodies, please revisit the main concerns/suggestions previously expressed by the external reviewers. Explain whether and if so what changes have been incorporated in the current proposal.

Main concerns/suggestions previously expressed by the external reviewers

Changes incorporated in the current proposal

13. Please indicate whether this application has previously been submitted to the Research Grants Council (RGC), i.e. a General Research Fund (GRF) application: (where appropriate)

- (i) the current FRG application is a project independent of the GRF;
- (ii) the FRG is a pilot study in preparation for the GRF;
- (iii) the FRG forms part of the GRF and the application is seeking seed funding for the GRF
- (iv) the FRG and the GRF is one and the same project.

Has the proposed GRF secured any funding from the RGC?

- Yes No

If the answer is yes, please give the following figures:

(a) Original Requested Amount of GRF Project:

(b) Approved Amount of GRF Project:

(c) Top-up Funding Sought for GRF Project:

14. Declaration

If the total of the approved funding for the GRF project (b), top-up funding for the GRF project (c) and the requested amount for the current FRG (d) i.e. (b)+(c)+(d)=(e) exceeds that of the GRF original requested amount (a), the PI agrees to reimburse to the Specialist Panel the difference between the funding for the GRF/FRG [i.e. (e)] and the GRF original requested amount (a), i.e. (e)-(a)=(f) being the reimbursement to the Specialist Panels. This declaration is to prevent double funding in view of the scarcity of resources.

15. Have you submitted any HKBU-endorsed RGC related schemes such as GRF / ECS/ CRF / PPR / SPPR / TBRS / AoE / ANR / ESRC / NSFC (or equivalent) proposals as PI in the immediate past year? If no, please note Annex C “Variable Quota for FRG Projects” to see whether you are eligible for FRG application.

Submission(s) in 2014/15

Scheme	Ref No	Grant Title
ECS	22601015	Stage-Specific Prediction of Physical Activity Adoption and Maintenance: A Prospective Evaluation Study in Elderly People in Hong Kong

16. Number of On-going FRG Projects held by the PI in the capacity of PI (Refer to Annex C for “Variable Quota System for FRG Projects”) (including those of which completion reports have not yet been submitted. where appropriate)

0

1 Project Code: _____

2 Project Code: _____

>2 Project Code: _____

17. Details of on-going research projects (including those of which completion reports have not yet been submitted) funded by whatever sources undertaken by all investigator(s):

Chinese Medicine and Science Panel applicants: Provide also a list of FRG, RGC or other projects which PI **has completed** within the previous 2 years.

Name of investigator(s) (Indicate PI or Co-I)	Project title and project code	Grant & source(s) (HK\$)	Starting date	Expected completion date	Amount of time involved (hours/week)
[name](PI)	Time-Limited Reduced Earning Capability Pension and Return To Work	\$800,000 German Pension Insurance Institution Bremen	1 Jun 2015	31 May 2017	5
[name](PI)	Prevention of reduced working ability with an Expert System with telephone, motivational interviews supporting self-management	\$650,000 German Pension Insurance Institution Bremen	1 Sep 2014	31 Aug 2016	5

18. List of Outstanding FRG (Cat I & II) Completion Reports:

Project Code	Project Title	Starting Date	Completion Date	Report Submission Date (6 months from Completion Date)

19. Plans for collaboration:

(This item should be completed if two or more co-investigators are involved in the project.)

(Indicate the division of work among the PI, co-investigator(s) and research support staff and the amount of time [hours per week] each is expected to spend on this project. The role of each individual should be adequately described).

The PI, Co-Is and research assistant basically work as a team in developing the research plan. However, in carrying out the study, the job specifications for each investigator are as follows:

[name], the PI, would be responsible for overseeing the entire research project, including the formulation of research design, selection and recruitment of subjects, conducting data collection and analyses, writing of the final report, and supervising the research assistant. She is expected to spend an average of 8 hours/week on the project.

[name], the Co-I, would be contributing her expertise in research design, data statistical analyses and writing of the research report. She is expected to spend an average of 3 hours/week on the project.

[name], [name] and [name], the Co-Is, would be contributing their networking in the recruitment of students in their general PE classes, and facilitating students' engagement on this program. Each of them is expected to spend an average of 2 hours/week on this project.

A full-time research assistant would assist website set-up and function test, main study implementation (4 months), data management and analysis, and report writing. She/he is expected to spend an average of 40 hours/week on this project.

20. International Collaboration (applicable to ARTS/SOSC/COMM/BUS/AVA)

Please provide the following supplementary information below:

- (a) a description and value of the collaboration;
- (b) connection to international institutions;
- (c) statement of outcome;
- (d) scope or potential for future collaboration;

N/A

21. Research ethics/safety approval:

Please tick '✓' the appropriate box(es) to indicate approval required, if any, from the Senate Committee on the Use of Human and Animal Subjects in Teaching and Research (HASC).

(If "none" is the response, please indicate also.)

Human Research Ethics	
Animal Research Ethics	
Biological Safety	
Ionizing Radiation Safety	
Non-Ionizing Radiation Safety	
Chemical Safety	
None	

* If approval is required, download form(s) from the Graduate School Homepage:

- (1) HASC's Ethics (Animal) Questionnaire - HASC/ETHICS/ANI (involving ANIMAL subjects)
- (2) HASC's Ethics (Human) Questionnaire - HASC/ETHICS/HUM (involving HUMAN subjects) (New)
- (3) HASC's Safety Questionnaire (HASC/SAFETY) (New) (please note Sections 4 and 5 in particular for Chemical Safety)

**** Please note proposals from ALL Specialist Panels should first seek relevant ethical/safety approval from the HASC before the Panels can make the funding decision.**

22. Curriculum vitae of investigators:

(Please submit a brief CV* for all investigators relevant to the proposed area of research. - **one CV for each separate proposal.**)

* The brief CV should contain the following information only:

- (i) education background;
- (ii) employment history;
- (iii) publication list (for the previous 5 years.)
(**Chinese Medicine & Science Panel applicants** - indicate publications or submitted manuscripts arising from your previous or ongoing projects.) and
- (iv) research activities (for the previous 5 years).

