We will examine whether the students in the two intervention groups improve their motivation for PA and healthy diets in comparison to the control group; whether, with the help of an intervention program, students are able to increase their PA levels and healthy diet consumption, and whether there are different effects between the two intervention programs. We believe the study findings will provide an e-health learning approach to support Chinese university students to maintain their health behavior in daily life.

4. The project aims, its long-term significance:

(State the aims, identify the key issues and problems being addressed and list the possible outcomes of the research project, as well as its significance and value) (Maximum 600 words or 1 page)

Key issues and problems:

A successful transition from late adolescence to adulthood is essential for university students. Physical activity and healthy diet can support this process and lead to positive health outcomes. However, considerable evidence has revealed a significant decline in PA behavior participation among university students worldwide (Vankim, Laska, Ehlinger, Lust & Story, 2010). Additionally, study in China revealed that approximately half of the university students do not eat fruits every day and one third of students do not eat dark vegetables for long time (Li, 2014). Such a pattern of unhealthy lifestyle habit, which is reinforced during university, has a significant effect on behavior and health in later adulthood (Epton, Norman, Dadzie et al., 2014). Therefore, it is critical for university students to be motivated to adopt and maintain healthy lifestyle during this transition period.

The project aims:

The aim of this project is to examine the effectiveness of two website & SMS prompts-based e-health learning courses (intervention groups I-II, IG-I: sequential first physical activity, then dietary; IG-II: sequential first dietary, then physical activity) compared to a control group condition. Individuals who participate in e-health learning programs should be encouraged to develop a healthy lifestyle in their daily life, with a primary focus being on motivation, behaviour change and quality of life.

The possible outcomes of the research project are to provide knowledge on:

1. Participants in the intervention groups (IGs) gain a higher motivation for physical activity and healthy diet in comparison with a control group.

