The level of PA will be measured with the short version of IPAQ questionnaire (Mäder, Martin, Schutz, & Marti 2006). Participants will be asked to estimate the amount of days and spend time for vigorous, moderate and walking activities during the past seven days. To assess the fruit and vegetable consumption during the past seven days, four items will be used. Participants will be asked to count the number of consumed portions or glasses fruit and vegetable a day. It will be distinguished between fruit, fruit/vegetable juice, cooked or steamed vegetable, and raw vegetable (Rafferty, Anderson, McGee, Miller, 2002).

4. Variables related to health

Compensatory health beliefs will be measured by 4 items with Cronbach's α = 0.55. (Knäuper, Rabiau, Cohen, & Patriciu, 2004). **Quality of life:** Respondents will be firstly asked about their general quality of life as "How would you rate your quality of life?", then 7 items in physical health subdomain will be used. (Cronbach's α = 0.89). (WHOQOL-BREF; World Health Organization, 1993).

Statistical analysis:

Data analysis will be performed using SPSS 21.0. Descriptive statistics will be used to describe the baseline characteristics in the study. We will assess whether there are significant differences between the intervention groups compared to the control group according to physical activity and nutrition by means of linear regression analysis in PASW.

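### The diet questionnaire does not say how a day with only fruit or only vegetables counts, and the Chinese form switches from 'and' to 'or' between the days and amount items

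*Combined protocol and SAP*

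**What the plan says.** Questionnaire Part II, item 2 (Dietary behaviour) has two questions in English. The days question is "On how many days during the last 7days have you been eaten fruits and vegetables". The amount question is "On those days you ate fruits and vegetables, how many portions do you eat", followed by the unit: "One portion accounts for approximately one hand of fruit or vegetable".

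The Chinese form, Part II, item 2, asks the days question as "您有几天吃过吃水果和蔬菜", which joins the foods with 和 (and). Its amount question asks for portions when the student eats fruit or vegetables, joined with 或 (or), and does not refer back to the days just counted.

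Section 6, Methodology, Measures (Past health Behaviour) describes a different instrument: "To assess the fruit and vegetable consumption during the past seven days, four items will be used". It continues "Participants will be asked to count the number of consumed portions or glasses fruit and vegetable a day" and "It will be distinguished between fruit, fruit/vegetable juice, cooked or steamed vegetable, and raw vegetable". The same section refers the reader to the attachment for the full questionnaires.

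Fruit and vegetable consumption is one of the behaviours in Objective 2. Under Statistical analysis it is a dependent variable in the MANCOVA, with baseline behaviours as covariates. No section says how the two questionnaire answers are combined into a score.

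**The concern.** A student who eats vegetables every day and fruit on three days can answer the days item with 3 (days with both foods) or 7 (days with either). Both answers fit the wording, and the data will not show which reading was used. Such days are unlikely to be rare: Section 4 (Key issues and problems) reports that "approximately half of the university students do not eat fruits every day".

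The Chinese form is presumably the one used at Wuhan and Nantong. There, a student who reads the days item strictly would report days with both foods and then an amount that covers days with either, so the two answers would describe different sets of days.

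What is at stake is measured change in a behavioural outcome. Under a strict reading, adding fruit on a vegetable-only day also brings in the vegetables already eaten that day. Adding vegetables on a day without fruit may not count at all.

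**Working it through.** The plan states no figure on this point, so there is none to reproduce. The check compares the wording and then illustrates what the ambiguity can do.

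**Wording**

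- English days item: 'and'. English amount item: 'and', tied to the same days. Portion unit: 'or'. The two English items share one frame, and the only gap is how a single-food day counts.
- Chinese days item: 和 (and). Chinese amount item: 或 (or). The connective changes between the items.
- Score: not stated for the two-item form. The Measures text describes portions or glasses a day from four items by food type.

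**Illustration.** All intakes are assumed; the documents give none. Weekly intake is taken as days × portions, also an assumption. The student starts with 2 vegetable portions daily and 1 fruit portion on 3 days. Three scores are compared:

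- (a) inclusive reading: 7 days × average portions per day, which equals true intake;
- (b) strict reading: days with both foods × portions on those days;
- (c) strict days × portions averaged over all eating days, which is possible with the Chinese wording.

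| Diet | (a) True | (b) | (c) |
|---|---|---|---|
| Start | 2×7 + 1×3 = 17 | 3×3 = 9 | 3×17/7 = 7.3 |
| Fruit becomes daily | 3×7 = 21 | 7×3 = 21 | 7×3 = 21 |
| One more vegetable portion daily, fruit still on 3 days | 3×7 + 1×3 = 24 | 3×4 = 12 | 3×24/7 = 10.3 |

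Level at the start: (b) is 1 − 9/17 = 47% too low, and (c) is 1 − 7.3/17 = 57% too low.

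Gain when fruit becomes daily:
- (a) 21 − 17 = 4
- (b) 21 − 9 = 12
- (c) 21 − 7.3 = 13.7

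Gain when a daily vegetable portion is added:
- (a) 24 − 17 = 7
- (b) 12 − 9 = 3
- (c) 10.3 − 7.3 = 3.0

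The first gain is overstated and the second understated.

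Two limiting cases, in portions per day:

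- No true change: 3 portions on each of 7 days, with both-food days rising from 4 to 5. The true difference is 0; score (b) gives (5×3 − 4×3)/7 = 0.43.
- Both foods every day: a true gain of 0.50 is measured as 0.50 under every score.

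So error in measured change requires single-food days, a strict reading and a product score, all three together. Its sign depends on which food was added.

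**The case against.** The strongest reply is that the strict reading is the less natural one. The questionnaire treats fruit and vegetables as one food category throughout, for instance in the five-portion target, and in Chinese the 'or' in the next item points towards the inclusive meaning. Under that reading no days are lost. This stands as a reason to expect that many students will answer as intended. It does not show that all will, and the answers cannot be checked afterwards.

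A second reply is that randomised arms answer the same item and baseline behaviour is a covariate. That disposes of a constant error in level. It does not dispose of an error in change whose scale depends on which food was added, as the gains of 12 for 4 and 3 for 7 show.

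A third is that the Procedure (Validation stage) already provides for adjusting the materials and testing students' understanding. It does, but with two students, who could easily miss this.

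Stronger readings are tempting, and the documents do not support them. A reader might infer that the plan itself multiplies days by portions; no scoring rule is given. A reader might infer a full and/or conflict in English; the English amount question repeats 'and'. A reader might take the background figure to mean that about half of students will be mismeasured; it says only that about half do not eat fruit daily, and mismeasurement also needs vegetables eaten on those days, a strict reading and a product score.

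**Conclusion.** The point holds as a defect of wording and definition. Neither language defines how a single-food day counts, the connective changes between the two Chinese items, and the score is not written down. This is the printed instrument for an Objective 2 outcome.

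It would go too far to conclude that the programme effect is distorted, or to give a factor for it. The share of students who would read strictly is unknown, the intakes above are assumed, and the illustrations run in both directions. Size and direction cannot be determined from the documents, and under the inclusive reading the error is zero. If the four items by food type under Measures are what will be used, this wording problem falls away.

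The correction is worth making because it is cheap now and cannot be made after T1.

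**What to change.** During the month 1-9 validation of the questionnaires:

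1. Word the days item as *fruit or vegetables (either or both)* in English and *水果或蔬菜（任一种或两种）* in Chinese.
2. Word the amount item in both languages as *on those days, how many portions of fruit and vegetables in total per day*, so that it refers to the days just counted.
3. Write the score formula into Statistical analysis, including how the lowest response category of the days item enters it.
4. Reconcile the two-item form with the four items by food type under Measures, and state which instrument yields the MANCOVA outcome and its baseline covariate.

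The cost is a few words in each language and one sentence on scoring. The downside is slightly less comparability with any data already collected with the present items.
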